Over 60% of the women who are diagnosed with breast cancer in the Netherlands are treated with systemic treatment, which may be administered before (neoadjuvant systemic therapy, NST) or after (adjuvant) locoregional treatment. Depending on the subtype, 10-75% of patients will have a pathologic complete response (pCR) after NST. In this patient group, risk of local recurrence is extremely low. The administration of adjuvant radiotherapy in these patients is not expected to contribute significantly to overall survival, but may cause considerable morbidity.

Objective:

Primary aim: to assess whether local recurrence is acceptable when radiotherapy is omitted after breast conserving surgery in patients treated with NST who achieve a pathologic complete response.

Secondary aim: to assess quality of life and cancer worry after omitting radiotherapy.

Study design:

DESCARTES is a national, multicentre, non-randomized, single-arm prospective cohort study.

Study population:

Patients >18 years with cT1-2, N0 HR+HER2-, HER2+(HR+/-) or TN breast cancer who are treated with breast conserving surgery and achieve pathologic complete response.

Intervention:

Omitting radiotherapy following breast-conserving surgery.

Main study parameters/endpoints:

The primary endpoint is the local recurrence rate (LRR) at 5 years. Secondary determinants are local non-salvageable recurrence free survival, quality of life, regional recurrence rate, distant recurrence free survival, disease-specific survival and overall survival.

Nature and extent of the burden and risks associated with participation, benefit and group relatedness:

The immediate impact for participants is to be spared intensive radiotherapy and subsequent risk of side effects (such as pain, fatigue, possible lung damage). An expected 4% will develop a local recurrence within 5 years, about half of which would not have happened with standard radiotherapy. The majority of these local recurrences can however effectively be treated with salvage breast-conserving or ablative surgery and previous studies indicated that patient survival will not be affected.

1. INTRODUCTION AND RATIONALE

NST is increasingly used in breast cancer treatment(1), resulting in tumour downsizing and increase in breast conserving surgery(BCS) rates without compromising local recurrence or overall survival.(2-6) The extent of tumour downsizing is largely dependent on breast cancer molecular subtypes with highest pCR rates in triple negative(TN) and HER2+ subtypes (40-88%) and pCR rates of 10-15% in HR+/HER2- breast cancer.(7-14)

De-escalating locoregional treatment following NST cannot be achieved by omitting surgery, since biopsies or MRI do not accurately assess pCR. (15-17). Adjuvant whole breast irradiation however may be de-escalated in pCR patients who do not have an indication for regional irradiation.(18)

In this patient group, risk of distant and local failure is low. Mamounas first reported retrospectively on cT1-3N0-2 patients treated with NST in two major clinical trials conducted from 1988 to 1993 and from 1995 to 2000. Only 10-year results on local recurrence were reported. In 225 clinically node-negative patients with pCR, local recurrence was 5.2 and 6.9% for patients >50 and <50 years respectively.(19) Notably, pCR definition included patients with residual in situ disease and axillary lymph node status was defined by palpation only. As the large majority of local recurrences occur within 5 years from treatment, especially in Her2 positive and triple-negative breast cancer, the reported 10-year recurrences will have included new primary cancers.(20) However, this overview confirmed that the absence of pCR was the most important predictor for locoregional recurrence with a hazard ratio of 2.77.(19)

Recent studies including up-to-date systemic treatments and pre-NST staging with MRI and axillary ultrasound report considerably lower 5 year recurrence rates, as shown in Table 1. All studies include patients with stage I-III disease and include residual DCIS in pCR definition. Samples sizes for pCR patients vary between 157 and 426, with **local** recurrence rates between 1.0-3.5%, with isolated tumour cells considered pCR in the highest reported recurrence. **Locoregional** recurrence rates in pCR patients range from 0.0%-3.2%.(21-23) Swisher et al report recurrence rates per molecular subtype, with lowest rates in hormone receptor positive breast cancer.(22) Notably, 61% of patients in this cohort presented with node-positive disease, but LRR was not specified for cN0 versus cN+ patients.(22)

Even more recent studies investigating risk factors for DFS and OS in patients achieving a pCR, have reported poorer outcomes for patients with ypTis compared to ypT0, cN+ compared to cN0 and cT3/4 compared to cT1/2. (24-25) Although ypTis is considered a risk factor for poorer outcomes, it is expected that not all patients with DCIS in pre-NST biopsy have the same prognosis. A study by Groen et al. demonstrated that DCIS can

DESCARTES study

respond well to NST and reported several risk factors associated with response of DCIS to NST; calcifications on mammography prior to NST, treatment with dual HER2+ blockade and absence of calcifications or Ki67>20% in pre-NST biopsy. (26)

Author		сТММ	Molecular subtype				pCR	5-year in- breast recurrence	
Chen et al.(10)	1987-2000	T1-4N0-1*	not specified		157	BCT + RT	Unknown**	1%	3%
Vila et al.(11)	1997-2005	T0-4N0-3	not specified		656	BCT + RT	Unknown	2.9%	5.5%
Vila et al. (11)	1997-2005	T0-4N0-3	not specified		250	BCT + RT or Mx +/- RT	Yes, pTis included	-	3.2%
Swisher et al.(12)	2005-2012	T0-4N0-3	All		243	BCT + RT	Yes, pTis included	-	1.0%
				HR+/HER2-	61	BCT + RT	Yes, pTis included		0%
				HR+/HER2+	48	BCT + RT	Yes, pTis included		0%
				HR-/HER2+	42	BCT + RT	Yes, pTis included		2.6%
				HR-/HER2-	92	BCT + RT	Yes, pTis included		1.4%
Gillon et al.(13)	2001-2006	T1-4N0-3	All		1553	mastectomy / BCT + RT	Unknown	1.9%	4.9%
					283	mastectomy / BCT + RT	Yes, pTis and pTitc included	3.5%	
					426	mastectomy / BCT + RT	Yes, pCR of lymph nodes		2.3%

Table 1. Local and locoregional recurrence rates following NST; *patients with noninflammatory breast cancer excluded and ** no LVI, pCR or solitary residual invasive tumour of <2 cm

A recent study reports on locoregional recurrence following NST when radiotherapy is omitted. In this series, 197 cT1-4N0-3 patients with pCR following NST and treated with BCS were included, 110 of which did not receive adjuvant radiotherapy.(27) Notably, 57% of patients included in the study presented with node-positive disease and patients with residual in situ disease were considered as pCR. Five year local recurrence rates **without radiotherapy** are 0% for luminal and HER2 subtype, 3.1% for TNBC and 3.2% for luminal HER2+ breast cancer (Table 2.(27) (results obtained via personal communication with author)

		BCS foll	owed by RT	BCS without RT		
Molecular subtype		Total (N)	5-year LR (%)	Total (N)	5-year LR (%)	
All		87	1.1%	110	1.8%	
	Luminal	8	0 (0%)	16	0 (0%)	
	LuminalHER2+	19	0 (0%)	31	1 (3.2%)	
	HER2+	18	0 (0%)	31	0 (0%)	
	TNBC	42	1 (2.4%)	32	1 (3.1%)	

Table 2. Local recurrence rates for pCR patients treated with NST and breast conserving surgery. For pCR definition, ypTis was included.

The effect of omitting radiotherapy on survival was investigated by Mandish et al. in 5383 patients with cT0-4, N0-3 breast cancer treated with NST and breast conserving surgery who showed pCR of both breast and lymph nodes. Of these patients, 364 did not receive adjuvant radiotherapy. This did not compromise survival, as 5-year OS rates did not significantly differ (93.6% with RT and 93% without RT, adjusted hazard ratio 1.33, 95% CI 0.76-2.31, p=0.3181).(28)

Radiotherapy of the breast is associated with both short-term and long-term morbidity in up to 50% of patients(29-32. Radiotherapy negatively influences quality of life by long-term morbidity consisting of secondary lung cancer, cardiac mortality, painful fibrosis of the breast and impaired cosmetics.(29-34) De-escalating local therapy by partial breast and hypofractionated radiotherapy was shown to positively impact quality of life by reducing fibrosis and breast deformation.(35-37) Omitting radiotherapy altogether in patients with extremely low risk of local recurrence is already implemented for a group of older patients with low risk of recurrence following primary surgical treatment (*NCT03375801)(TOP-1*). This results in increased local recurrence rates without compromising survival.(28,38, 39)

As the relation between radiotherapy and long-term side effects of breast conserving treatment is thus well established, omitting radiotherapy altogether can be assumed to further improve breast-specific quality of life. We therefore propose a single-arm study in which radiotherapy is omitted in eligible patients.

2. OBJECTIVES

Primary Objective:

To show that omitting radiotherapy in patients with a pathologic complete response to NST results in a 5-year local control rate of >94%.

Secondary Objective:

To show that omitting radiotherapy in patients with a pathologic complete response to NST results in good quality of life without compromising cancer worry levels.

To assess the 5- and 10-year local control rate, distant- and regional metastasis free survival and local non salvageable recurrence free survival.

3. STUDY DESIGN

The DESCARTES trial is a prospective single arm study investigating the effects on local control and quality of life of omitting radiotherapy after NST in cT1-2N0 patients who achieve breast and axillary pCR after NST. Eligibility of patients will be assessed at multi-disciplinary meetings.

Women with any type of invasive breast cancer are eligible for inclusion. Patients with a history of breast cancer, DCIS or LCIS are excluded. Concurrent DCIS in pre-NST biopsy is allowed if there is no suspicion of an extensive component; patients are excluded if they have the combination of concurrent DCIS in pre-NST biopsy and calcifications on pre-NST mammography and/or non-mass enhancement on pre-NST MRI, contrast-enhanced mammography or breast-specific gamma imaging. Concurrent LCIS of any type in pre-NST biopsy is not allowed. A marker should be placed in the center of the tumour before start of NST. Contrast- enhanced breast MRI, a contrast-enhanced mammography or breast-specific gamma imaging is conducted pre-NST for reliable assessment of unifocal disease. Axillary status is evaluated by ultrasound. In case of suspicious axillary lymph node(s), fine needle aspiration is performed for cytology analysis to confirm node-negative disease. Following NST, breast conserving surgery is performed. A post-NST sentinel node biopsy procedure (if not performed pre-NST) is performed using single or dual-tracer technique. The surgical specimen will be assessed by a specialized breast pathologist according to national

guidelines. A pathologic complete response is defined as ypT0N0 (i.e. absence of invasive carcinoma and in-situ carcinoma in breast and axilla). In case One-Step Nucleid Acid Amplification (OSNA) is used to determine status of sentinel node, only negative OSNA results will be accepted as N0.

If pCR of breast and lymph nodes is present (ypT0N0), patients may be entered into the single-arm study, in which radiotherapy of the breast is omitted. Adjuvant systemic therapy is administered according to national breast cancer guidelines.

Patients will be followed yearly for a period of 5 years and at 10 years to assess localregional recurrence. Quality of life (QOL) is measured using the Patient Reported Outcome Measures (PROMs), which are integrated in standard care in the Antoni van Leeuwenhoek and other centers, and additional questionnaires containing measure not included in the standard PROMS set. The PROMs include the EORTC-QLQ-C30 and EORTC-QLQ-BR23. The 8-item Cancer Worry Scale will be used to measure if worry related to omission of radiotherapy may affect QOL. Two demographic variables (education level and tolerance for uncertainty) will be measured at baseline as these patient characteristics could be associated with quality of life and level

DESCARTES study

of experienced cancer worry and need to be considered in the analyses. The additional QOL questionnaires are provided simultaneously with the PROMs: the first are provided for baseline measurement, and the following are provided at 1 year and 4 years after surgery. See table 3 for an overview of the QOL measurements.

All recurrences should be confirmed with pathology analysis. All lesions suspect for disease recurrence are discussed at multidisciplinary meetings, according to clinical practice guidelines.

*Sentinel node biopsy may be performed before start of neoadjuvant systemic therapy

Figure 1. Descartes trial study design

	PROMs	Additional QOL questionnaires
Baseline	EORTC-QLQ-C30, EORTC- QLQ-BR23	Education level, 12-item Intolerance of uncertainty scale, Cancer Worry Scale
1 year after surgery	EORTC-QLQ-C30, EORTC- QLQ-BR23	Cancer Worry Scale
4 years after surgery	EORTC QLQ-C30	Cancer Worry Scale, EORTC-QLQ-BR23

4. STUDY POPULATION

4.1 Population (base)

Eligible patients are women with cT1-2, N0 HR+HER2-, HER2+(HR+/-) or TN breast cancer who achieve pathologic complete response after NST. Concurrent DCIS in pre-NST biopsy is allowed if there is no suspicion of an extensive component; patients are excluded if they have the combination of concurrent DCIS in pre-NST biopsy and calcifications on pre-NST mammography and/or non-mass enhancement on pre-NST MRI, contrast-enhanced mammography or breast-specific gamma imaging. Concurrent LCIS of any type in pre-NST biopsy is not allowed. Patients are clinically node negative in the absence of suspect nodes on ultrasound and/or FDG-PET/CT, or the absence of tumour cells at cyto-/histopathology in patients with suspect nodes on ultrasound and/or FDG-PET/CT pre-NST. A marker should be placed in the tumour before start of NST and adequate position should be confirmed by mammography or ultrasound. In case of suspicious axillary lymph node(s), fine needle aspiration is performed for cytology analysis.

4.2 Inclusion criteria

In order to be eligible to participate in this study, a subject must meet all of the following criteria:

- Women, aged \geq 18 years
- Invasive HR positive/Her2 negative, Her2+ (ER/PR +/-) or TN breast cancer
- Concurrent DCIS in pre-NST biopsy is allowed if there is no suspicion of extensive component i.e. absence of non-mass enhancement on pre-NST MRI, contrastenhanced mammography or breast-specific gamma imaging and/or absence of calcifications on pre-NST mammography
- Primary tumour (T) clinical stage cT1-2
- Unifocal disease; confirmed by pre-NST MRI, contrast-enhanced mammography or breast-specific gamma imaging
- Clinical nodal stage 0; absence of lymph node metastases should be confirmed by ultrasound or FDG-PET/CT
- Neoadjuvant systemic treatment (NST)
- Marker placed in breast tumour prior to NST
- Breast conserving surgery performed, i.e. no mastectomy
- Sentinel node biopsy performed before or after NST
- Pathologic complete response in breast and lymph nodes, i.e. no residual tumour cells, DCIS or LCIS detected
- Written informed consent within 16 weeks following the date of surgery

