4.3 Exclusion criteria

A potential subject who meets any of the following criteria will be excluded from participation in this study:

- Primary tumour (T) clinical stage cT3-4
- Pre- or post-NST diagnosis of nodal disease including isolated tumour cells
- Concurrent LCIS of any type in either pre-NST biopsy or surgical specimen
- Patients without axillary ultrasound or FDG-PET/CT pre-NST
- History of breast cancer, DCIS or LCIS
- Synchronous contralateral breast cancer, DCIS or LCIS
- Synchronous M1 disease
- Carrier of gene mutation associated with increased risk of breast cancer, i.e. BRCA1, BRCA2, CHEK2, TP53 or PALB-2

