10. ADMINISTRATIVE ASPECTS, MONITORING AND PUBLICATION

10.1 Handling and storage of data and documents

The central data management will be performed by the Netherlands Cancer Institute-Antoni van Leeuwenhoek. Registration will be done after the written informed consent is obtained and after verification of eligibility. After the written informed consent is obtained, patients will be assigned to a registration number.

Registration will be performed using ALEA® registration package run by the NKI Data Center.

All data that are relevant for the study will be collected on eCRFs developed by the NKI data Center. The system can be accessed via internet to include data directly in the Data Centre Servers. The AVL Datacenter will supply accounts to the local data manager to enter data into the system. Checks will be incorporated into the eCRF system to prompt queries at the moment that data is entered facilitating the work of the local data manager who could quickly correct errors. Additional checks will be programmed using statistical programs with the goal of obtaining a clean file.

The time between the patient's visit and completion of eCRF pages should be kept to a reasonable minimum allowing answering the questions posed by the study. In all cases it remains the responsibility of the investigator to check and validate the data after verifying that they are completed and filled out correctly. If information is not known, this must be clearly indicated.

The investigator will retain all pertinent information for a period of at least 15 years from study completion.

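### The biopsy-DCIS item in Section 4.2 is not the mirror image of the exclusion in Sections 3 and 4.1: read literally, it admits patients with one imaging sign whom those sections exclude

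*Protocol*

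**What the plan says.** Three sections of the protocol state a rule on DCIS found in the biopsy before neoadjuvant systemic therapy (NST).

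- **Section 3 (Study design):** "patients are excluded if they have the combination of concurrent DCIS in pre-NST biopsy and calcifications on pre-NST mammography and/or non-mass enhancement" on the listed contrast or gamma imaging.
- **Section 4.1 (Population):** the same exclusion, for the combination of "concurrent DCIS in pre-NST biopsy and calcifications on pre-NST mammography and/or non-mass enhancement on pre-NST MRI" or the alternative imaging methods.
- **Section 4.2 (Inclusion criteria):** biopsy DCIS is acceptable when an extensive component is not suspected. An 'i.e.' then defines this as absence of non-mass enhancement on MRI, contrast-enhanced mammography or "breast-specific gamma imaging and/or absence of calcifications on pre-NST mammography".

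Section 4.2 is introduced as a list of necessary conditions: "a subject must meet all of the following criteria". Section 4.3 (Exclusion criteria) has an item for the other in-situ lesion, "Concurrent LCIS of any type in either pre-NST biopsy or surgical specimen", but no counterpart for ipsilateral DCIS in the biopsy. There, DCIS appears only as history or as synchronous contralateral disease.

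On process, Section 3 says "Eligibility of patients will be assessed at multi-disciplinary meetings", and Section 10.1 says "Registration will be done after the written informed consent is obtained and after verification of eligibility". Neither says which section's wording applies.

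**The concern.** The opposite of 'calcifications or non-mass enhancement' is 'no calcifications **and** no non-mass enhancement'. Section 4.2 negated each sign but left 'and/or' between them. Taken literally, the absence of one sign is then enough, although Sections 3 and 4.1 treat the presence of one sign as disqualifying.

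The item is operative, because a patient who passes the lists enters a single-arm study in which radiotherapy is omitted. With no control arm, the 5-year local recurrence result is interpretable only for a clearly defined population. As written, the same patient could be called eligible or a protocol deviation, depending on the section consulted.

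**Working it through.** No figure in the protocol is at issue, so the check is a truth table. Let D = DCIS in the pre-NST biopsy, C = calcifications on mammography, N = non-mass enhancement.

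**Step 1. Rules with 'and/or' read inclusively.**

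- Sections 3 and 4.1 exclude if D and (C or N).
- Section 4.2 is met if not D, or if (not N) or (not C).

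**Step 2. The four combinations with D present.**

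| Imaging signs | Sections 3 and 4.1 | Section 4.2 | Agree? |
|---|---|---|---|
| Neither | allowed | met | yes |
| Calcifications only | excluded | met | **no** |
| Non-mass enhancement only | excluded | met | **no** |
| Both | excluded | not met | yes |

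Section 4.2 admits 3 of 4 combinations and Sections 3 and 4.1 admit 1 of 4, a difference of 2. The four combinations without D produce no conflict, so 2 of all 8 combinations conflict.

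**Step 3. Dependence on how 'and/or' is read.** Sets admitted among patients with D:

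| Reading in 3 and 4.1 | Admitted by 3 and 4.1 | Reading in 4.2 | Admitted by 4.2 | Same set? | Admitted by all sections jointly |
|---|---|---|---|---|---|
| or | neither | or | neither, C only, N only | **no** | neither |
| and | neither, C only, N only | and | neither | **no** | neither |
| or | neither | and | neither | yes | neither |
| and | neither, C only, N only | or | neither, C only, N only | yes | neither, C only, N only |

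Whenever the connector has the same meaning in both places, the sections disagree on the same two one-sign groups. With 'or' throughout, Section 4.2 is the looser rule. With 'and' throughout, it is the stricter one. The sections match only if the connector changes meaning between them.

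**Step 4. Other parses.** Grouping the exclusion as (D and C) or N still excludes both one-sign patients who have D. An exclusive 'or' in Section 4.2 still admits them. Neither removes the conflict.

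**Step 5. Do the formal lists catch the one-sign patient elsewhere?** Section 4.3 does not. The requirement for a pathologic complete response without DCIS does so only when DCIS remains in the surgical specimen. A one-sign patient with a clear specimen passes both lists.

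**Step 6. Joint application.** Since the 4.2 items are necessary rather than sufficient, applying Sections 3, 4.1 and 4.2 together admits only the patient with neither sign in three of the four pairings of readings. The conflict therefore arises when the lists are used without Sections 3 and 4.1.

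**The case against.** Several points count against the concern.

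- **The protocol already states the exclusion twice.** Sections 3 and 4.1 give it in the same words, and someone reading the whole document would exclude the one-sign patient on the ordinary reading. This stands. The problem is an internal contradiction, not a missing rule, and the document does not show that sites differ.
- **Two of the four pairings of readings show no conflict.** This is correct, as Step 3 shows. Both pairings, however, need one connector to mean 'or' in one section and 'and' in another, which a site cannot be expected to infer.
- **The lead phrase in Section 4.2 governs.** Biopsy DCIS is acceptable only without suspicion of an extensive component, so a clinician must still use judgement. That would carry weight if the imaging clause were an example. It follows 'i.e.', so it is the stated definition of the phrase.
- **The connector is used loosely elsewhere.** The node-negative definition in Section 4.1 also pairs absence with 'and/or' across ultrasound and FDG-PET/CT, evidently without meaning that one clear test overrides a suspect one. This makes a wording slip the likely explanation, but it does not make the 4.2 item unambiguous.
- **The consequence is limited.** Residual DCIS excludes the patient anyway, and eligibility is reviewed at multidisciplinary meetings and verified before registration. The first is a real limit. The second helps only if the reviewers know which wording applies.

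**Conclusion.** The concern holds as a drafting inconsistency in an operative eligibility criterion. On the inclusive reading, the 4.2/4.3 lists used alone admit two groups that Sections 3 and 4.1 exclude: biopsy DCIS with calcifications only, and biopsy DCIS with non-mass enhancement only. That conclusion assumes that 'and/or' means the same in each section. It does not assume that any site has enrolled such patients.

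The number affected cannot be derived from the protocol, so no effect on the expected 4% or acceptable 6% recurrence rate can be calculated. The sample size, power and alpha are untouched. It should be corrected because the item decides who enters a study without radiotherapy, but it does not undermine the design.

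**What to change.** Reconcile Sections 3, 4.1 and 4.2 to one identical rule. Replace 'and/or' with an explicit 'and' or 'or', remembering that the connector must switch when an exclusion is rewritten as an absence condition. For example, an exclusion for 'C or N' corresponds to an inclusion requiring 'no C and no N', and an exclusion for 'C and N' corresponds to 'no C or no N'. Either matched pair leaves 0 of the 8 combinations in conflict. Carry the same rule into the formal 4.2/4.3 lists so that they give the full answer when used alone. Which rule is intended is for the sponsor to decide.

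The cost is a wording change. Depending on the rule confirmed, the eligible pool may be somewhat smaller than the present lists imply. The protocol gives no basis for estimating by how much.
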